### 11.2.5 FreeLite™ Disease Response Criteria

**Complete Response:** For those patients being followed by serum free light chain (and NO measurable serum or urine M-spike), which were immunofixation negative at enrollment, normalization of serum free light chain ratio.

- Normalization is defined as the serum free light chain ratio being within the normal range. If the serum free light chain ratio is not within the normal range, but the individual kappa and lambda light chain values are within normal range, this may be considered CR.

**Partial Response:** If only measurable parameter is serum immunoglobulins free light chain (FLC), EITHER of the following changes qualify as partial response:

- A 50% decrease in the difference between involved and uninvolved FLC levels; OR
- A 50% decrease in the level of involved FLC AND a 50% decrease (or normalization) in the ratio of involved/uninvolved FLC

**Progressive Disease:** If only measurable parameter is serum immunoglobulins free light (FLC), either of the following qualify as progression:

- 50% increase in the difference between involved and uninvolved FLC levels from the lowest response level, which must also be an absolute increase of at least 10 mg/dL; OR
- 50% increase in the level of involved FLC AND a 50% increase in the ratio of involved/uninvolved FLC from the lowest response level.

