## 10. STUDY CALENDAR

Screening evaluations are to be conducted within 28 days prior to initiation of registration. Protocol therapy should start as soon after registration as feasible. Baseline assessments are to be conducted on C1D1 of initial therapy and should be considered separate from screening evaluations. Evaluations need not be repeated for C1D1 if screening evaluations are performed within 7 days of registration. Scans and bone marrow assessments do not need to be repeated if performed within 6 weeks of registration. All assessments must be performed prior to administration of any study medication.. See below for detailed scheduled of assessments. Study medications will be administered according to the schedule and guidelines outlined in Section 5.

	Pre-registration		Cycles 1-24 (28 days) 				Follow Up 
Tests and procedures	≤ 28 days prior to registration	≤ 21 days prior to registration	Day 1 of all cycles	Days 8, 15 and 22 of cycles 1 & 2	Cycle 9 Day 1/ Or to confirm CR^9	End of Tx	Every 3 or 6 Months (+/- 28 days)
				Days 1 &15 from cycle 3-8			
History and exam, height, weight. Performance Status	X		X			X	(X)
Toxicity Notation			X			X	
Hematology group (WBC w/ diff, PLT, Hgb, ANC)		X	X	X		X	X
Chemistry 		X	X	X		X	X
Direct & total bilirubin 		X	X			X	
Free light chain assay		X	X			X	X
Serum and Urine Immunofixation (SPEP and UPEP) with quantitative immunoglobulins 		X	X			X	X
β2M, CRP, LDH		X				X	
Metastatic Bone Survey/ Spine MRI or PET/CT 	X					X	(X)
EKG		X				X	
Serum pregnancy test		X					
Unilateral bone marrow aspirate and biopsy 	X				X	X	(X)
Research bone marrow aspirate 	X 				X 	X 	(X)
Research Blood 	X 		X		X	X	(X)

1- Cycle 1, Day 1 laboratory values need to meet eligibility criteria

2- Direct bilirubin to be obtained if total bilirubin is abnormal.

3- Scheduling allows for +/- 3 days cycles 1-2 and +/- 7 days for cycle 3 and beyond.

4- Chemistry includes sodium, potassium, chloride, bicarbonate, bun, creatinine, calcium, glucose, albumin, ALT (SGPT), total protein, AST (SGOT), total bilirubin, magnesium, and phosphorus.

5- These procedures should also be done at any time during the course of the study to confirm CR.

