#### **For measurement of response:**

In this study, patients must have measurable disease. The disease response will be assessed using criteria based on the International Working Group Uniform Response Criteria in Section 11.2.4. If the only measurable parameter is serum immunoglobulins free light chain (FLC), the participant will be followed by FreeLite™ Disease Response Criteria provided in Section 11.2.5.

Disease response by the Modified EBMT Response Criteria in Section 11.2.6.2 will also be collected on participants as a secondary measure.

**The same method of assessment and technique should be used for disease measurement at baseline and during follow-up. Disease response should be confirmed by two consecutive**

CONFIDENTIAL

This document is confidential. Do not disclose or use except as authorized.

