### 11.2.2 Methods for Evaluation of Measurable Disease

All baseline evaluations should be performed on Cycle 1, Day 1 of initial therapy. Response will be assessed by M-protein quantification, protein electrophoresis and immunofixation from serum and a 24-hour urine collection. A serum sample for FreeLite™ testing will be obtained. In addition, bone marrow aspiration and biopsy, as well as skeletal survey will be performed to determine overall response or confirm response.

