### 11.2.4 International Myeloma Working Group Response Criteria

Response criteria for all categories and subcategories of response except CR are applicable

CONFIDENTIAL

This document is confidential. Do not disclose or use except as authorized.

only to patients who have ‘measurable’ disease, as defined in Section 11.2 All response categories require two consecutive assessments made at any time before the institution of any new therapy; all categories also require no known evidence of progressive or new bone lesions if radiographic studies were performed. Radiographic studies are not required to satisfy these response requirements.

**Stringent CR:** CR as defined below plus normal free light chain ratio and absence of clonal cells in bone marrow\* by immunohistochemistry or immunofluorescence.\*\*

\*Confirmation with repeat bone marrow biopsy is not needed.

\*\*Presence/absence of clonal cells is based upon the  $k/\lambda$  ratio. An abnormal  $k/\lambda$  ratio by immunohistochemistry and/or immunofluorescence requires a minimum of 100 plasma cells for analysis. An abnormal ratio reflecting presence of an abnormal clone is  $k/\lambda$  of  $> 4:1$  or  $< 1:2$ .

**CR:** Negative immunofixation on the serum and urine and disappearance of any soft tissue plasmacytomas and  $\leq 5\%$  plasma cells in bone marrow.

\*Confirmation with repeat bone marrow biopsy is not needed.

**VGPR:** Serum and urine M-protein detectable by immunofixation but not on electrophoresis or 90% or greater reduction in serum M-protein plus urine M-protein level  $< 100\text{mg}$  per 24 hours.

**PR:**  $\geq 50\%$  reduction of serum M-protein and reduction in 24-h urinary M-protein by  $> 90\%$  or to  $< 200\text{mg}$  per 24 hours. If the serum and urine M-protein are unmeasurable, a  $\geq 50\%$  decrease in the difference between involved and uninvolved free light chain levels is required in place of the M-protein criteria (definition of measurable disease in Section 10.2.3). If serum and urine M-protein are unmeasurable, and serum free light assay is also unmeasurable,  $\geq 50\%$  reduction in plasma cells is required in place of M-protein, provided baseline bone marrow plasma cell percentage was  $\geq 30\%$ . In addition to the above listed criteria, if present at baseline, a  $> 50\%$  reduction in the size of soft tissue plasmacytomas is also required.

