#### 11.2.6.2 Modified EBMT Response Criteria

Response	Criteria for Response a
Complete response (CR)	Requires all of the following:  Disappearance of the original monoclonal protein from the blood and urine on at least two determinations for a minimum of six weeks by immunofixation studies.  <5% plasma cells in the bone marrow on at least two determinations for a minimum of six weeks. b  No increase in the size or number of lytic bone lesions (development of a compression fracture does not exclude response). c  Disappearance of soft tissue plasmacytomas for at least six weeks.
Near Complete Response (nCR)	Requires the following:  Same as CR, but immunofixation studies continue to show presence of the monoclonal protein
Very Good Partial Response (VGPR)	Requires the following: $\geq 90\%$ reduction in serum M-protein plus urine M-protein level <100mg per 24 hours on at least two determinations for a minimum of six weeks.

CONFIDENTIAL

This document is confidential. Do not disclose or use except as authorized.

Partial response (PR)	
PR includes participants in whom some, but not all, criteria for CR are fulfilled providing the remaining criteria satisfy the requirements for PR. Required all of the following:
 
≥50% reduction in the level of serum monoclonal protein for at least two determinations six weeks apart.
 
If present, reduction in 24-hour urinary light chain excretion by either ≥90% or to <200 mg for at least two determinations six weeks apart.
 
≥50% reduction in the size of soft tissue plasmacytomas (by clinical or radiographic examination) for at least six weeks.
 
No increase in size or number of lytic bone lesions (development of compression fracture does not exclude response).c

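### Section 11.2.5 sets no marrow plasma-cell limit for a complete response defined by free light chains, so a patient with persistent clonal marrow can be counted as CR

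*Combined protocol and SAP*

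**What the plan says.** Section 11.1, under measurement of response, assigns the criteria: "If the only measurable parameter is serum immunoglobulins free light chain (FLC), the participant will be followed by FreeLite" criteria in section 11.2.5. That section gives the CR rule for patients with no measurable serum or urine M-spike as "immunofixation negative at enrollment, normalization of serum free light chain ratio". It adds a second route for a ratio that stays abnormal, "but the individual kappa and lambda light chain values are within normal range, this may be considered CR". Neither route mentions the marrow.

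The protocol's other two CR definitions do. Section 11.2.4 asks for "Negative immunofixation on the serum and urine and disappearance of any soft tissue plasmacytomas and" no more than 5% plasma cells in the marrow. The modified EBMT table in section 11.2.6.2, collected as a secondary measure, asks for fewer than 5% "plasma cells in the bone marrow on at least two determinations for a minimum of six weeks".

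Marrow sampling itself is planned for everyone. Section 11.2.2 says that "bone marrow aspiration and biopsy, as well as skeletal survey will be performed to determine overall response or confirm response". Footnote 5 of the study calendar, attached to the marrow aspirate and biopsy, says "These procedures should also be done at any time during the course of the study to confirm CR". Appendix C also lists a marrow aspirate at confirmation of CR.

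Section 13.1.2 reports the proportion in CR with a 90% exact interval and does not distinguish the criteria by which CR was reached. Section 11.2.6 measures minimal residual disease (MRD) in patients who achieve CR.

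**The concern.** Every patient enters under section 3.1.2 with at least 10% clonal marrow plasma cells. Patients covered by the 11.2.5 CR rule are already immunofixation negative at entry, so the immunofixation part of the 11.2.4 definition cannot show any change in them. The marrow limit is the part that could show clearance, and it is the part that 11.2.5 leaves out.

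If the rule is applied as written, one reported CR proportion mixes two outcomes: remission that includes the marrow, and light-chain normalization whatever the marrow shows. The same label decides who enters the MRD assessment. The second route is discretionary, and section 11.2.9 plans no central review of response, so sites could score identical patients differently.

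**Working it through.** **1. The three CR definitions side by side**

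| Section | Serology | Marrow plasma cells |
|---|---|---|
| 11.2.4 (IMWG) | Serum and urine immunofixation negative | ≤5% |
| 11.2.6.2 (EBMT, secondary) | Original monoclonal protein absent by immunofixation | <5% |
| 11.2.5 (FLC only) | Ratio normal, or abnormal with both chains in range | None stated |

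**2. Tracing one patient through the text.** Take a patient who enters with 10% clonal marrow plasma cells, no measurable M-protein, negative immunofixation, and an involved FLC level that is measurable under section 11.2.1. The ratio normalizes and is confirmed on a second assessment. The confirmatory marrow still shows 10%.
- Against the 11.2.4 limit: 10% > 5%, not CR.
- Against the EBMT limit: 10% > 5%, not CR.
- Under 11.2.5: CR.

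**3. Looking for a passage that settles it.** Calendar footnote 5, section 11.2.2 and Appendix C call for a marrow but give no threshold for an FLC-defined CR. Appendix C refers to section 11.2.3 for the definition of CR, and that section only requires a confirmation measurement. Stringent CR in 11.2.4 adds a normal FLC ratio to a CR that already includes the marrow limit, so the main criteria do not treat a normal ratio as a substitute for marrow clearance.

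**4. The plan's own response figure.** Section 13.1.2 says that the exact 90% interval is no wider than 28% with 39 eligible patients. The Clopper-Pearson limits for x of n are the 5% quantile of Beta(x, n−x+1) and the 95% quantile of Beta(x+1, n−x). Over x = 0 to 39 the widest interval is 28.1%, at x = 20. The stated figure reproduces.

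**5. Effect on the CR proportion.** If k patients are scored CR under 11.2.5 without meeting a marrow limit, the proportion rises by k/n. The documents give no value for k, so the values below are assumptions. Both 39 (eligible patients, section 13.1) and 55 (total enrolment, section 13.2) are shown.

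| k (assumed) | n = 39 | n = 55 |
|---|---|---|
| 0 | 0 | 0 |
| 1 | 2.6 points | 1.8 points |
| 2 | 5.1 points | 3.6 points |
| 4 | 10.3 points | 7.3 points |

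As an illustration with an assumed 12 CRs in 39: 12/39 = 30.8% (90% interval 18.8% to 45.0%). Removing two gives 10/39 = 25.6% (14.6% to 39.6%).

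**6. What does not move.** The primary rule (24 or more of 39 progression free at 2 years) does not use response. A patient moved out of CR ordinarily still meets an 11.2.5 PR route, such as a 50% fall in the difference between involved and uninvolved chains, so PR or better is unchanged.

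**The case against.** The strongest reply is that 11.2.5 replaces only the serologic part of CR. Section 11.2.4 exempts CR from its restriction to measurable disease and carries its own FLC provisions for partial response and progression, so its 5% limit could be read as binding FLC-only patients too. That reading is possible. But section 11.1 sends these patients to 11.2.5, which states a complete CR rule without a marrow condition. The conflict is unresolved, and that in itself calls for a clarifying sentence.

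Other parts of the reply stand and limit the point:
- A reader might infer that no marrow is required at all. The documents do not support this: a marrow is called for at CR, and only the threshold is missing.
- A marrow-based EBMT CR is collected in parallel. It is a secondary measure and does not change a classification under 11.2.5.
- A reader might take this to cover every light-chain patient. It does not. Section 2.5 marks monoclonal light-chain disease by urinary excretion of 500 mg/24 h or more, above the 200 mg/24 h that counts as measurable in section 11.2.1. Such patients fall outside the 11.2.5 CR rule.
- The MRD result is not made to look better. MRD at CR is measured on marrow, so a patient with persistent clonal marrow would be expected to test positive. The effect is on who enters the set, not on an inflated MRD-negative count.

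**Conclusion.** The gap is real and confined to a definition. Section 11.2.5 lets CR be scored on light chains without a marrow threshold, while the protocol's other two CR definitions have one. The CR proportion could be overstated by 2.6 points per affected patient at n = 39, or 1.8 at n = 55. This assumes that 11.2.5 is applied literally and that the patient's marrow would fail the 5% limit.

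A reader might infer that the CR rate is overstated, for example by 5 to 15 points if 2 to 6 of 39 patients were affected (2/39 = 5.1%, 6/39 = 15.4%). The documents do not support that. They give neither the share of FLC-only patients nor how often marrow disease persists after FLC normalization, and the number affected may be zero.

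The consequence is limited to a descriptive secondary proportion and to entry into the MRD assessment. The primary endpoint is untouched, and the PR-or-better rate ordinarily is too.

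**What to change.** In section 11.2.5, state that CR also requires the 11.2.4 marrow limit (no more than 5% plasma cells) on the confirmatory marrow already scheduled. Replace the discretionary wording for an abnormal ratio with a fixed rule under the same marrow condition. Patients whose light chains normalize without marrow clearance are then scored by the existing 11.2.5 partial-response rule.

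If the sponsor does intend an FLC-only CR, say so, and report those patients separately from the 11.2.4 CRs with their marrow results.

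The cost is one or two sentences and no new procedure. The reported CR rate may be slightly lower.

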**Elotuzumab and Lenalidomide Maintenance Therapy (Cycles 9-24)**

Agent	Premedication and Precautions	Schedule	Dose	Route	Cycle Length
Elotuzumab	Premedications are described below	Days 1 of each cycle	20 mg/kg	Intravenous-See appendix B for more details	
Lenalidomide	None	Days 1-21 of each cycle	15 mg	Oral	28 days (4 weeks)
Dexamethasone*	Take with food; recommended to be taken in the morning	Day 1 of each cycle	8 mg	IV	
			28 mg	Oral	

\* After discussion with the overall PI, high-dose dexamethasone may be re-added during maintenance due to biochemical progression (progressive increase in SPEP [25% and an absolute increase of 0.5g/d] or UPEP [25% and an absolute increase of 200mg/24hours] on 2 successive evaluations as determined by the IMWG response criteria or documented progression by the FreeLite™ progressive disease criteria in the absence of serum or urine involvement). Dexamethasone should be given as follows after overall PI approval:

Day	Dose	Route
1	8 mg	IV
	32 mg	Oral
8	40 mg	Oral
15	40 mg	Oral

CONFIDENTIAL

This document is confidential. Do not disclose or use except as authorized.

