**SD:** Not meeting criteria for CR, VGPR, PR or progressive disease. This is not recommended as an indicator of response; stability of disease is best described by providing the time to progression estimates.

**PD:**  $> 25\%$  increase of serum M-protein (which must also be an absolute increase of  $\geq 0.5\text{ g/dL}$ ) and/or urine M-protein (which must also be an absolute increase of  $\geq 200\text{ mg/24hr}$ ). If serum and urine M-protein are unmeasurable, there must be an absolute increase of  $\geq 10\text{ mg/dL}$  between involved and uninvolved FLC levels. PD is also measured by an absolute increase in bone marrow plasma cells  $\geq 10\%$ . In addition to the above listed criteria, progression may also be measured by a definite development of new bone lesions or soft tissue plasmacytomas or definite increase in the size of existing bone lesions or soft tissue plasmacytomas or development of hypercalcemia (corrected serum calcium  $\geq 11.5\text{ mg/dL}$  or  $2.65\text{ mmol/L}$ ) that can be attributed solely to the plasma cell proliferative disorder.

CONFIDENTIAL

This document is confidential. Do not disclose or use except as authorized.

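### The second FLC progression limb in 11.2.5 has no absolute minimum, so in patients measurable only by FLC it can call a very small low-level rise progression where 11.2.4 would not

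*Combined protocol and SAP*

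**What the plan says.** Section 11.1 assigns patients to criteria. If FLC is the only measurable parameter, "the participant will be followed by FreeLite™ Disease Response Criteria provided in Section 11.2.5". Section 11.2.1 sets the FLC measurability limit at an involved level of at least 10 mg/dL with an abnormal ratio.

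Under progressive disease, 11.2.5 states that "either of the following qualify as progression":

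- Limb 1 is a 50% rise in the involved-minus-uninvolved difference from its lowest level, "which must also be an absolute increase of at least 10 mg/dL; OR"
- Limb 2 is a "50% increase in the level of involved FLC AND a 50% increase in the ratio of involved/uninvolved FLC from the lowest response level".

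The progression paragraph of 11.2.4 also covers these patients: "If serum and urine M-protein are unmeasurable, there must be an absolute increase of" at least 10 mg/dL between the involved and uninvolved levels.

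Complete response in 11.2.5 applies to FLC-followed patients who were immunofixation-negative at enrolment. It requires a normalized ratio: "Normalization is defined as the serum free light chain ratio being within the normal range". There is also a permissive alternative when the ratio is abnormal: if "the individual kappa and lambda light chain values are within normal range, this may be considered CR".

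The footnote to the maintenance table in 5.1 uses "documented progression by the FreeLite™ progressive disease criteria in the absence of serum or urine involvement" as one trigger for discussing re-addition of high-dose dexamethasone.

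**The concern.** Limb 2 is sufficient alone and purely relative. The other percentage-based progression criteria all carry an absolute minimum: serum and urine M-protein in 11.2.4, the same pair in the 5.1 footnote, the serum, urine and marrow items of the modified EBMT table, and limb 1 itself. Relative criteria need that protection most at a low reference value, and limb 2 counts from the lowest response level. In a good responder that level can lie far below the protocol's own measurability limit.

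Two things follow for a patient measurable only by FLC. The same pair of assays can be progression under 11.2.5 and not under 11.2.4. In some of these patients the same sample can also meet the FLC definition of complete response, and nothing in 11.2.5 makes the two categories mutually exclusive.

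A false progression ends duration of response (11.2.7). It is also an event for TTP and PFS wherever biochemical progression is what counts. Central review of response is not planned (11.2.9), so sites will apply the words as written.

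**Working it through.** The plan gives no figure for this rule, so there is none to reproduce. The check is logical first, then illustrative.

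**Inputs from the documents:** the two limbs and the complete-response rule (11.2.5); the 10 mg/dL requirement (11.2.4, read as a rise in the involved-minus-uninvolved difference); FLC assayed on Day 1 of each of 24 cycles (section 10).

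**Not in the documents:** normal ranges, assay CV, correlation between chains, and the number of FLC-only patients.

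**Step 1: smallest rise that meets limb 2.** Let I0 be the nadir involved FLC and hold the uninvolved chain U constant. The ratio I/U then rises by the same factor as I, so one change satisfies both parts of limb 2 once I1 ≥ 1.5 × I0. The difference rises by I1 − I0 = 0.5 × I0. This reaches 10 mg/dL only if I0 ≥ 10 / 0.5 = 20 mg/dL. Below 20 mg/dL the sections can disagree: 19.9 rising to 29.85 is +9.95 mg/dL, which is progression by limb 2 but not by 11.2.4.

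**Step 2: a low nadir (assumed values).** Involved FLC goes from 0.8 to 1.25 mg/dL with uninvolved FLC at 0.8.

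- Involved: 1.25 / 0.8 = 1.56, a rise of 56%.
- Ratio: 1.00 to 1.56, a rise of 56%.
- Difference: 0 to 0.45 mg/dL, about 1/22 of 10 mg/dL.

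Limb 2 is met; limb 1 and 11.2.4 are not.

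**Step 3: overlap with complete response.** The second sample in step 2 can also meet FLC complete response if the patient was immunofixation-negative at enrolment and the ratio, or both chains, lie in the laboratory's normal range. A rise of 50% can stay inside any range whose upper limit is at least 1.5 times its lower limit.

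**Step 4: illustrative size.** The simulation takes a truly stable responder with both chains at the same normal-level mean (about 1.2 mg/dL), lognormal noise, a running nadir, 24 monthly assays, and limb 2 met on two consecutive assays. The table gives the approximate chance of false progression.

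| Assumed CV per chain | Independent chains | Correlation 0.5 | Correlation 0.8 |
|---|---|---|---|
| 5% | 0% | 0% | 0% |
| 10% | 1% | 0.1% | 0% |
| 15% | 32% | 12% | 0.2% |
| 20% | 72% | 49% | 8% |
| 25% | 90% | 77% | 30% |

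With 12 assays at nadir and correlation 0.5, the figures at CV 10% to 25% are about 0%, 2.7%, 15% and 33%. With the 10 mg/dL minimum added to limb 2, the result is 0% in every scenario.

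**The case against.** The strongest reply is that 11.1 already settles which text applies: FLC-only patients follow 11.2.5, so the FLC sentence in 11.2.4 could be a redundant leftover. That is a fair reading, and it rules out calling this an irreconcilable contradiction. However, 11.2.4 nowhere says that it yields, and limb 2 would still lack a minimum.

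The overlap with complete response is narrower than a reader might infer. It is confined to patients who were immunofixation-negative at enrolment, one route is only permissive, and no normal ranges are given. Section 2.4 also describes the involved chain as the one above its reference range, so limb 2 might be thought not evaluable once both chains are normal. Fixing the involved chain at baseline is equally natural, and 11.2.5 does not say which is meant.

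A reader might infer that everyone with light-chain smoldering disease is affected, since 3.1.2 does not exclude them. It does not follow. Section 2.5 characterises light-chain disease by excretion of at least 500 mg/24 h, above the 200 mg/24 h urine limit in 11.2.1, so those patients have measurable urine disease. FLC-only patients enter through 11.1 and 11.2.1, and among 55 enrolled they may be very few.

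Two-assessment confirmation is stated for response categories but not explicitly for progression in 11.2.5. If it applies, it lowers the false rate, as the table already assumes, but it sets no minimum.

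Finally, the consequences are qualified elsewhere. Section 11.1 names symptomatic myeloma as the final endpoint, with an FLC event at a ratio of at least 100 (or at most 0.01). The 5.1 footnote provides for biochemical progression during maintenance after discussion with the overall PI, so such progression does not automatically mean removal under 5.5.

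**Conclusion.** The drafting gap stands. Limb 2 is the only percentage-based progression criterion without an absolute minimum. For a patient measurable only by FLC it can disagree with 11.2.4 at any nadir below 20 mg/dL, taking uninvolved FLC as constant. Overlap with complete response is possible but conditional on enrolment immunofixation and on the laboratory's ranges.

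The size is not established. The table runs from 0% to 90% on assumed CV and correlation alone. It also supposes a responder who sits at normal-level values for all 24 assays, although a patient measurable under 11.2.1 starts at 10 mg/dL or more and must first respond. A reader might take the 32% to 90% column entries as the expected error rate; they belong to independent chains with a CV of 15% or more, and the documents support neither assumption.

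Nor do the documents support a claim that the 2-year progression-free rate is biased. That depends on whether biochemical progression or symptomatic myeloma is the event, a separate ambiguity between 11.1 and the definitions in 11.2.4 and 11.2.8. Duration of response in FLC-only patients is the clearest exposure, followed by TTP and PFS to the extent that biochemical progression counts. This is worth correcting, with reach limited to an unstated and possibly small subgroup.

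**What to change.** For endpoint classification (duration of response, TTP and PFS), either extend to limb 2 the absolute increase of at least 10 mg/dL in the involved-minus-uninvolved difference, which limb 1 and 11.2.4 already contain, or drop limb 2. State in 11.2.4 that FLC-only patients are classified by the amended 11.2.5.

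The cost is one sentence in 11.2.5 and one cross-reference. No new samples are needed, and FLC values already collected can be reclassified. The small downside is that an occasional true low-level relapse would be dated slightly later.

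The same definition also feeds treatment decisions in the 5.1 maintenance footnote and in 5.5. The sponsor should reconcile those passages with 11.2.4 and 11.2.5; no clinical rule is proposed here.
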